Enrollment will be monitored and potentially capped to ensure that the study enrolls an aggregate of at least 75% of HCWs who are taking a potential prophylactic therapy.

For details on the information collected and the overall study design, refer to [Table 1](#), [Table 2](#), [Figure 1](#), and [Figure 2](#), respectively.

This is a comparative observational cohort study; therefore, no preventive interventions, visits or laboratory tests are mandated. Dosing and duration of potential prophylactic treatment is at the discretion of the institution and/or healthcare provider, in accordance with regular local practice. However, serology testing for SARS-CoV-2 antibodies may be offered to approximately 50% of participating HCWs per country, at enrollment (ranging from baseline up to Week 4 [African countries] and Week 8 [Pakistan]) and at the last follow-up (i.e. at Week 12).

Figure 1 Study Schematic - High-level

HCW: Healthcare Worker

Figure 2 Study Schematic – Healthcare Worker Flow

[figure not shown]

Table 1 Schedule of Assessments – Healthcare Worker Flow

Variable domain	At Enrollment		Weekly follow-up (until Week 12) ^c	
	HCW	HCW	Secondary Contact	
Inclusion/eligibility criteria (screening questions/index date)	X	-	-	-
Electronic/paper (if applicable) consent	X	-	-	-
Demographics	X	-	-	-
Underlying conditions	X	-	-	-
Job characteristics	X	-	-	-
BCG vaccination history	X	-	-	-
Household history (COVID-19)	X	X	-	-
COVID-19 exposure	X	X	-	-
Prophylactic treatments	X	X	-	-
Concomitant medications	X	X	-	-
COVID-19 vaccination ^e	X	X	-	-
PPE	X	X	-	-
COVID-19 symptoms	X	X	-	-
SARS-CoV-2 testing	X	X	-	-
Serology testing ^f	X	X ^b	-	-
WHO Ordinal Scale for Clinical Improvement ^d	X	X	-	X ^a

BCG: Bacillus Calmette–Guérin; CoV: Coronavirus; HCW: Healthcare worker; PPE: Personal Protective Equipment; SARS: Severe acute respiratory syndrome; WHO: World Health Organization.

^a: In case HCWs stop responding (after due diligence reminders), their secondary contacts will be approached. In case of conflicts, responses by HCWs will be considered.

^b: Testing to be requested at last (Week 12) follow-up.

^c: Or, time since last follow-up, whichever is greater.

^d: Adapted, abbreviated version.

^e: From the time the questions on vaccination go live in the web application online survey, baseline vaccination information will only be collected for newly enrolled HCW and for HCWs who did not complete the survey prior to the addition of vaccination questions.

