8.3 Variables

The sections below include outcomes, treatment exposure and PPE use, COVID-19 exposure, COVID-19 vaccinations, and other variables to be measured and accounted for in the study analyses. Refer to [Appendix 2](#) for further details.

8.3.1 *Clinical Outcomes Variables*

- WHO Ordinal Scale for Clinical Improvement of COVID-19 (adapted, abbreviated version)
 - SARS-CoV-2 (uninfected/infected)
 - Ambulatory status (limitation/no limitation of activities)
 - Hospitalized with no intensive care unit (ICU) or mechanical ventilation (mild)
 - Hospitalized with ICU and/or mechanical ventilation (severe)
 - Death

8.3.2 *Prophylactic Treatment (Treatment Exposure)*

- Types, intake frequency, and doses of prophylactic treatments
 - Treatment name
 - Date started
 - Date stopped
 - Dose (intake)
 - Duration of treatment
 - Dose frequency and dosing interval
 - Status (stopped/ongoing)
 - Reason for stopping (not available/side effects/expense/other)
 - Number of missed doses and reason (not available/side effects/expense/other)

8.3.3 *History of Exposure to COVID-19 Patients*

- At enrollment
 - Self-reported ongoing and recurrent exposure (yes/no)
 - WHO exposure definition (3 questions) (yes/no)
 - Direct patient care (yes/no)
 - Face-to-face contact (yes/no)
 - Present during aerosol-generating procedure (yes/no)
- Weekly follow-up
 - Self-reported ongoing and recurrent exposure (yes/no)
 - WHO exposure definition (3 questions) for past week

- Days worked past week
- Number of COVID-19 cases exposed to in the past week

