- Antiparasitics (yes/no). If yes, please specify.
 - Ivermectin (yes/no)
 - Other antiparasitics.
- Antiretrovirals for Human Immunodeficiency Virus (HIV) (yes/no). If yes, please specify.
 - Lopinavir
 - Ritonavir
 - Tenofovir
 - Nelfinavir
 - Other antiretrovirals
- Antivirals (yes/no). If yes, please specify.
 - Oseltamivir
 - Favipiravir
 - Arbidol
 - Anti-hepatitis C treatments
 - Remdesivir
 - Other antivirals
- Medication for high blood pressure and cardiovascular disease (yes/no). If yes, please specify.
 - Angiotensin-converting enzyme (ACE) inhibitor (e.g., lisinopril, enalapril)
 - Angiotensin II receptor blockers (ARB) inhibitor (e.g., losartan, irbesartan)
 - Other anti-hypertensive for high blood pressure
 - Other medicine for high blood pressure and cardiovascular disease (e.g., antiarrhythmics, inotropes, chronotropes)
- Nonsteroidal Anti-inflammatory Drugs (NSAIDs) e.g., Aspirin, Ibuprofen, Indomethacin, Celecoxib, Diclofenac (yes/no). If yes, please specify.
- Botanicals (yes/no)
 - Artemisia teas (COVID Organics)
- Immunocompromising drugs (yes/no). If yes, please specify.
 - Corticosteroids
 - Cancer chemotherapy

- Cyclosporine
- Drugs for autoimmune conditions such as lupus or rheumatoid arthritis, Crohn's disease
- Changes in concomitant medications.
- COVID-19 vaccinations
 - Convidicea (Ad5-nCoV)
 - CoronaVac (Sinovac)
 - Covaxin (BBV152)
 - EpiVacCorona (Vector Institute)
 - Janssen Pharmaceuticals (Johnson & Johnson) (Ad26.COV2.S)
 - Moderna COVID-19 Vaccine
 - Novavax (NVX-CoV2373)
 - Oxford-AstraZeneca COVID-19 Vaccine
 - Pfizer-BioNTech COVID-19 Vaccine
 - Sinopharm BBIBP-CorV
 - Sputnik V COVID-19 Vaccine
 - Other (to be specified)

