Pneumonia	X	X	-
Nausea or vomiting	X	X	-
Headache or migraine	X	X	-
Abdominal pain (pain in tummy)	X	X	-
Asthenia (weakness or loss of strength)	X	X	-
Arthralgia (joint pain)	X	X	-
Anosmia (loss of smell)	X	X	-
Ageusia (loss of taste)	X	X	-
Blue coloring in toes	X	X	-
Diarrhea (two or more looser-than-normal stools in 24 hours)	X	X	-
SARS-CoV-2 testing			
Tested? (yes/no)	X	X	-
Type of test	X	X	-
PCR (positive/negative)	X	X	-
Antigen test (positive/negative)	X	X	-
Serology (IgG and/ or IgM, positive/negative or titer)	X	X	-
Date of test	X	X	-
Serology testing	X	X	-
Household history (COVID-19)			
Number of household contacts	X	X	-
Additional household member(s) exposed to COVID-19 (yes/no) If yes, how many?	X	X	-
Additional household member(s) with symptoms consistent with COVID-19 (yes/no) If yes, how many?	X	X	-
Additional household member(s) diagnosed with COVID-19 (yes/no) If yes, how many?	X	X	-
Underlying conditions and key morbidities			
Chronic lung disease	X	-	-
Diabetes mellitus	X	-	-
Cardiovascular (heart) disease	X	-	-
Chronic renal (kidney) disease	X	-	-
Chronic liver disease	X	-	-
Immunocompromised condition (HIV/AIDS, organ transplant, other)	X	-	-
Tuberculosis	X	-	-
Neurologic/neurodevelopmental	X	-	-
Hypertension (high blood pressure)	X	-	-
History of stroke	X	-	-
Other chronic diseases	X	-	-
If female, currently pregnant	X	-	-
If female, currently breastfeeding/lactating	X	-	-
Job characteristics			
Type of healthcare work	X	-	-

Primary work location (ED, ICU, Medical floor)	X	X	-
Number of hours with patients	X	X	-
Concomitant medications (other than for COVID-19)			
Antibiotics (yes/no)	X	X	-
Antimalarials (yes/no)	X	X	-
Antiparasitics (yes/no)	X	X	-
Antiretrovirals for HIV (yes/no)	X	X	-
Antivirals (yes/no)	X	X	-
Medication for high blood pressure and cardiovascular disease (yes/no)	X	X	-
Nonsteroidal Anti-inflammatory Drugs (NSAIDs) (yes/no)	X	X	-
Botanicals (yes/no)	X	X	-
Immunocompromising drugs (yes/no)	X	X	-
COVID-19 vaccine (to be selected as applicable)			
Convidicea (Ad5-nCoV)	X	X	
CoronaVac (Sinovac)	X	X	
Covaxin (BBV152)	X	X	
EpiVacCorona (Vector Institute)	X	X	
Janssen Pharmaceuticals (Johnson & Johnson) (Ad26.COV2.S)	X	X	
Moderna COVID-19 Vaccine	X	X	
Novavax (NVX-CoV2373)	X	X	
Oxford-AstraZeneca COVID-19 Vaccine	X	X	
Pfizer-BioNTech COVID-19 Vaccine	X	X	
Sinopharm BBIBP-CorV	X	X	
Sputnik V COVID-19 Vaccine	X	X	
Other (please specify)	X	X	

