6.1 Overview.....	17
6.2 Missing values.....	18
6.2.1 Missing values for non-outcome variables	18
6.2.2 Missing values for outcomes.....	18
6.3 Descriptive analyses.....	18

6.3.1	Facility characteristics.....	19
6.3.2	Demographic characteristics.....	19
6.3.3	Household characteristics.....	20
6.3.4	Exposure to COVID-19 patients.....	20
6.3.5	Medical history.....	21
6.3.6	Medications for non-COVID-19 related purposes.....	22
6.3.7	Prophylactic medications.....	23
6.3.8	PPE usage	24
6.3.9	COVID-19 symptoms.....	25
6.4	Primary analysis	26
6.4.1	Frailty model: mixed effect Cox regression	26
	Table 5.4.1.....	26
6.5	Secondary analysis	27
6.6	Subgroup analyses	28
6.7	Sensitivity analyses	28
7	Minimization of study bias.....	30
7.1	Selection bias	30
7.2	Survival bias	30
7.3	Recall bias.....	30
7.4	Information bias.....	30
7.5	Indication bias.....	30
7.6	Protopathic bias	31
8	References	31
9	Appendix.....	32
9.1	Shell tables.....	33
	Table 8.2.1 COVID-19 exposure status among all screened healthcare workers.....	33
	Table 8.2.2 Primary and Secondary Outcomes at baseline and follow-up among the overall population	34
Table 8.2.3	Static Variables by COVID-19 indication	35
Table 8.2.4	Household characteristics at baseline by COVID-19 indication.....	37
Table 8.2.5	COVID-19 exposure at baseline by COVID-19 indication	39
Table 8.2.6	Comorbidities at baseline by COVID-19 indication.....	40

Table 8.2.7 Concomitant medications at baseline by COVID-19 indication.....	41
Table 8.2.8 Prophylaxis use.....	43
Table 8.2.9 PPE usage at baseline.....	44

1 Introduction

The purpose of this statistical analysis plan (SAP) is to provide an analytic framework for the study “International Registry of Healthcare Workers Exposed to COVID-19 Patients (UNITY Global)”. This SAP addresses the statistical analyses that will be carried out in support of the protocol objectives. This analysis plan is based on the protocol version 1.0 of the study dated 08 June 2020.

2 Objectives of the study

This is an international registry of HCWs exposed to SARS-CoV-2 while caring for confirmed or clinically diagnosed COVID-19 patients. The aim of this registry is to generate real-world evidence in HCWs to potentially inform recommendations and policies on prevention measures, including prophylactic use of potential drug therapies in HCWs.

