6.2 Missing values

6.2.1 Missing values for non-outcome variables

For descriptive analyses, each variable will be described with frequencies of missing and “Not Known” values. Outliers will be included in description as part of presenting ranges and percentiles (25th and 75th).

In case of partial dates, the following transformations will be made to estimate time frames and durations:

- If only month and year are indicated, “15” will be added for day
- If only year is indicated, “01” will be added for day and “07” for month

If this decision implies negative duration or inconsistencies, it will be reviewed case by case. Otherwise, the date will be considered missing. The possibility of using multiple imputation will be explored, if required during analysis, to address missing data, and subsequently evaluated with sensitivity analyses.

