6.3 Descriptive analyses

Prior to implementing the analysis to address the primary objectives of the study, descriptive analyses will be carried out to understand the main features and patterns in the population and in the data collected. Study population characteristics will be tabulated at index date.

WHO Ordinal Scale for Clinical Improvement (see Appendix 1) scores distribution over time will be displayed. Kaplan-Meier estimates will be calculated, and curves plotted for each time-to-event outcome.

The observed incidence weekly rates of PCR-confirmed or symptomatic COVID-19 and of COVID-19-related hospitalizations and deaths will be tabulated over weeks by facilities and compared according to

prophylactic treatment use (yes/no; by treatment, subject to sufficient sample size; and by pre- and post-exposure (to COVID-19 patients) use, subject to sufficient sample size).

Applications of estimated propensity scores will be employed to explore differences between HCWs' profiles exposed versus non-exposed to potential prophylactic treatments. Propensity scores will be estimated for receipt of potential prophylactic treatments based on key covariates of interest for the HCWs' profiles (age, gender, race, type of HCW, BMI, smoking status, medical history). Estimated propensity score distributions will be displayed over weeks and a concordance analysis performed to detect any trend over time.

Stratified pooled analyses at country level will also be displayed.

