Time-varying Covariates	Others in household exposed to COVID-19 infected individuals, Others in household showing symptoms of COVID-19, Others in household diagnosed with COVID-19, Number of COVID-19 infected patients exposed to, Direct care to COVID-19 patients, Face-to-face contact of COVID-19 patients, Present when aerosol generating procedures performed, Mask usage, Gown usage, Eye protection usage, Glove usage
-------------------------	--

Note: The necessity to create composite variables or collapse categories within variables will be determined upon the completion of the descriptive analyses. A correlation analysis will be completed to assess the level of correlation between variables, if a high level of correlation is found only one of the variables will be included as a covariate in the models.

A Cox model with mixed effects can be formulated as $h_i(t) = h_0(t) \exp(\mathbf{X}_i B + \alpha_j)$, where α_j denotes the random effect associated with the j -th cluster. The random effect can be thought of as a random intercept that modifies the linear predictor, while the shared frailty term has a multiplicative effect on the baseline hazard function: $h_i(t) = h_0(t) \exp(\alpha_j) \exp(\mathbf{X}_j B)^3$.

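### The SAP rests on protocol v1.0 and plans no use of COVID-19 vaccination, which protocol v1.1 collects weekly, so the adjusted hazard ratio as specified omits a potential time-varying confounder

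*SAP*

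**What the plan says.** **Protocol v1.1 (11 June 2021).** Section 8.3 introduces its variables as including "COVID-19 exposure, COVID-19 vaccinations, and other variables to be measured and accounted for in the study analyses". Section 8.3.5, Other Covariates, has an entry "COVID-19 vaccinations" that lists products by name. Table 1 and Appendix 2 mark vaccination for collection at enrolment and at each weekly follow-up. Footnote e of Table 1 limits the baseline item: "baseline vaccination information will only be collected for newly enrolled HCW and for HCWs who did not complete the survey" before the vaccination questions were added. Section 8.7.4, the primary analysis, speaks of exposure to prophylaxis, exposure to patients and other covariates, and does not name vaccination.

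**SAP.** Section 1 states: "This analysis plan is based on the protocol version 1.0 of the study dated 08 June 2020". Section 6.4.1 fits a Cox model with a subject-level random effect. Candidate covariates come from Table 5.4.1 and pass a univariate screen at p<0.20, then backward elimination to 0.10. Only facility and country stay in regardless. The time-varying candidates end with "Present when aerosol generating procedures performed, Mask usage, Gown usage, Eye protection usage, Glove usage". The descriptive propensity score in section 6.3 uses "age, gender, race, type of HCW, BMI, smoking status, medical history". For missing covariates, section 6.2.1 says only: "The possibility of using multiple imputation will be explored, if required during analysis, to address missing data".

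**The concern.** The registry is meant to inform policy on prophylactic drugs, and its main result is an adjusted hazard ratio for prophylaxis. Vaccination can change week by week within a person. It may be linked to infection risk and to the choice to take a prophylactic drug. The protocol was amended to collect it, but the document that should say how it enters the analysis was written against the earlier protocol. Two results are affected:

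- **Primary.** The adjusted hazard ratio has no prespecified adjustment for vaccination.
- **Secondary.** The analysis of factors that modify COVID-19 risk (SAP 6.5) tests only covariates left in the final primary model. A variable that never enters that model cannot be examined. This needs no assumption about confounding.

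**Working it through.** **1. Is vaccination anywhere in the SAP?** I looked in each place where it could appear.

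| SAP location | COVID-19 vaccination named? |
|---|---|
| 3.6, study variables | No (only facility BCG policy) |
| 6.3, descriptive analyses and propensity score | No |
| Table 5.4.1, time-fixed and time-varying covariates | No |
| 6.5 to 6.7, secondary, subgroup and sensitivity analyses | No |
| 7, bias | No |
| 9.1, shell tables | No |

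Sections 7.1 and 7.5 refer to inverse probability weighting in a section 5.4.2. No such section appears in the text, and the contents list runs from 6.4.1 to 6.5, so weighting does not fill the gap.

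**2. When does the omission bias the hazard ratio?** Two conditions are needed together:

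- Vaccination is associated with the measured outcome. SAP 3.5.1 defines a composite of tests, clinical diagnosis, symptoms and hospitalisation, from self-reported data. An association with symptom reporting or testing counts as well as one with infection risk.
- Vaccination differs by prophylaxis use after adjustment for facility, country and the other retained covariates.

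**3. How large could it be?** The documents give neither vaccine effect nor coverage, so every vaccine input here is my assumption. Let VE be the vaccine effect on infection, and v1 and v0 the residual vaccinated shares of person-time in users and non-users. An inert drug then shows

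RR = (1 − VE·v1) / (1 − VE·v0)

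| VE | 40% users, 30% non-users | Reversed |
|---|---|---|
| 30% | 0.88/0.91 = 0.97 | 1.03 |
| 50% | 0.80/0.85 = 0.94 | 1.06 |
| 70% | 0.72/0.79 = 0.91 | 1.10 |

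Equal coverage gives 1.00. If vaccines were available for only half of person-time, the middle column becomes 0.98, 0.97 and 0.96. These scenarios cover an effect on infection only, not one on reporting or testing.

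**4. What gap would imitate the planned effect?** Setting RR = 0.78 with v0 = 30% gives v1 = (1 − 0.78(1 − 0.3·VE))/VE. This is 97%, 67% and 55% for VE of 30%, 50% and 70%, or residual gaps of 67, 37 and 25 percentage points.

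**5. What can adjustment recover?** Footnote e leaves some HCWs without baseline status. Suppose they are coded as unknown and carry the same 40% against 30% gap, with VE 50%. In a large-sample Poisson model with 80% users, I assumed a risk of 10% in the unknown group and 5% in the rest. An inert drug then reads 0.98, 0.96 or 0.95 with 25%, 50% or 75% unknown. Swapping the two risks gives 0.99, 0.98 and 0.96. Without adjustment it reads 0.94. If those HCWs all precede vaccine roll-out, it reads 1.00.

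**6. What does restriction cost?** Reproduce the plan's power first. Protocol 8.7.7 and SAP 5 give N = 10,000, 20% unexposed, 10% risk and RR 0.78; SAP 6.1 gives two-sided 5%. Expected events are 2,000 × 0.10 + 8,000 × 0.078 = 824. Schoenfeld's formula, with 0.78 taken as the hazard ratio, gives

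Φ(√(824 × 0.2 × 0.8) × |ln 0.78| − 1.96) = Φ(0.893) = 81%

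This agrees with the stated 80%. With 412 events (N = 5,000) power is 52%, and with 206 (N = 2,500) it is 30%. The two smaller sizes are illustrative, because the number without baseline status is not given.

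**The case against.** The strongest reply has four parts.

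- **The table is open.** Section 6.4.1 calls Table 5.4.1 a list of covariates to be considered, so a later addition is not ruled out. That stands. But an unplanned addition is not a prespecified rule, and it would still face selection by p-value.
- **The protocol sets no modelling rule.** The sentence in 8.3 is general, and 8.7.4 does not name vaccination. A reader might infer that the SAP breaches a mandated adjustment; the documents do not go that far. Protocol 8.7 and 8.7.1 leave detailed methods and key variables to the SAP, and there the silence matters.
- **Facility and country absorb roll-out.** They absorb stable differences between sites. They do not absorb individual uptake within a facility or its change over time. Follow-up starts at first exposure or 7 days after treatment start, and Table 5.4.1 has no calendar term.
- **The SAP may simply be older.** Its title page is not available, so its date cannot be seen. Its country list matches v1.1 while its serology text offers testing to the first 50%, as before the amendment. A reader might infer a deliberate choice to leave vaccination out. The documents fit an incomplete update better.

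The role of vaccination is also less settled than 8.3.5 alone suggests. The amendment's rationale for collecting it refers to information on prophylactic treatments. Appendix 3 of the protocol and SAP 3.5.2 allow other treatments, so a vaccine entered as free text could be counted as exposure.

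**Conclusion.** The concern holds as an omission. The SAP has not been brought into line with protocol v1.1, and as written it uses COVID-19 vaccination in neither the primary hazard ratio nor the risk-factor analysis. Confidence in this is high.

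Confidence in the size of any bias is low. A reader might infer that the adjusted hazard ratio will be biased, or that vaccination could explain a result of 0.78. Neither follows. There is no bias if residual coverage is equal between users and non-users, and the direction cannot be told from the documents. Under the assumed 10-point gap and VE of 30% to 70%, the distortion is 3% to 9% downward or 3% to 10% upward. Imitating 0.78 takes a residual gap of 25 to 67 points if 30% of non-users are vaccinated.

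Nor is the sample-size statement at fault here: the stated 80% power agrees with the Cox-based calculation. This should be fixed before analysis.

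**What to change.** Revise the SAP as follows.

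1. Rebase it on protocol v1.1.
2. State the role of vaccination. Section 8.3.5 supports covariate status. If that is adopted, say how vaccines entered in the free-text treatment fields are handled.
3. As a covariate, add it to Table 5.4.1 as time-varying and keep it in the model regardless of the p<0.20 and 0.10 rules, as for facility and country. Add it to the propensity covariates. Define when a person counts as vaccinated, after checking whether the questionnaire records dates or doses.
4. State the primary-model rule for HCWs without baseline status under footnote e. An unknown category leaves some residual confounding, and the SAP should say so. Consider a calendar-period term, so that this category does not also absorb changes in incidence.
5. Add a sensitivity analysis restricted to HCWs whose status was captured from baseline.
6. Add a shell table of vaccination by prophylaxis use, as description and not as a test of residual confounding.

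**Cost.** A SAP revision with no new data collection. Adjustment stays incomplete for earlier enrolees, and the restricted analysis loses power: from 81% to about 52% or 30% if 5,000 or 2,500 HCWs remain.

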2.2 Secondary objectives

- To characterize the type of potential prophylactic treatments, by dose and duration, overall, and by country/region/site.
- To explore the key factors (for example, use of PPE, HCW and healthcare facility characteristics, underlying co-morbidities, household history and COVID-19 exposure) modifying the risk of COVID-19 among HCWs.

[figure not shown]
3 Study overview

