6.3.8 PPE usage

The following PPE usage of subjects included in the study will be descriptively summarized for HCWs with and without COVID-19 infection (see Table 8.2.9 in the appendix):

A stacked bar chart will be used to display PPE usage during the follow-up period. The x-axis will be dates of survey responses and the stacked bars will be grouped by yes/no (corresponding to PPE use at specific dates). This will be done separately for HCWs infected with COVID-19 and those uninfected. The stacked bar charts can be used to compare PPE use among infected/uninfected HCWs over time. This will be done for the four types of PPE (eg. masks, eye protection, gowns, gloves).

- PPE used in workplace since first known contact with COVID-19 patients
 - Mask (Yes always; Yes not always; No)
 - Type of Mask (N95 Respirator Mask; Other)
 - Eye Protection (Yes always; Yes not always; No)

- Gown (Yes always; Yes not always; No)
- Gloves (Yes always; Yes not always; No)
- The number of PPEs used as “yes always” among mask, eye protection, gown, gloves will also be summarized: none, one, two, three, all four

For HCWs with COVID-19 at entry: responses to the baseline survey will be used

For HCWs with COVID-19 at follow-up: overall PPE usage over the entire follow-up time available in the data cut. In addition, overall PPE usage in the 2 or 4 weeks (TBD) prior to COVID-19 infection date will be described.

For HCWs with no COVID-19 infection at any time: overall PPE usage over the entire follow-up time available in the data cut. In addition, overall PPE usage in the 2 or 4 weeks (TBD) prior to the data cut date will be described.

Overall PPE usage will be defined as the following from multiple weekly surveys being considered as above:

Responses seen in all weekly surveys being considered	Overall PPE usage
Yes always	Yes always
Yes always Yes not always	Yes not always
Yes always No	Yes not always
Yes always Yes not always No	Yes not always
Yes not always	Yes not always
Yes not always No	Yes not always
No	No

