6.4 Primary analysis

6.4.1 Frailty model: mixed effect Cox regression

For the time to COVID-19 infection outcome, both crude and adjusted hazards ratios will be estimated for time to COVID-19 infection with respect to prophylaxis use. The primary objective of this analysis is to assess the association between prophylactic treatments and the reduced risk of SARS-CoV-2 infection in HCWs caring for COVID-19 patients. A mixed effect Cox regression model (ie. frailty model) will be used to estimate adjusted hazard ratios. This method will allow the utilization of both the repeated measures gathered from each HCWs surveys, as well as the incorporation of time-varying covariates of interest such as PPE usage and COVID-19 exposure. Each subject will be included as a random effect. Both time-fixed and time-varying covariates will be included in the model. Covariates will be assessed using a univariate model, any covariates with a p-value less than 0.20 will be included in a multivariate model. A backward stepwise process will then be completed, where the covariates with largest p-value are removed one at a time until all covariates that remain are significant at the 0.10 level. The time-fixed covariates, healthcare facility and country will be included in the model regardless of their significance level. Including the healthcare facility and country covariates will make each healthcare worker's COVID-19 outcome conditionally independent on the background COVID-19 incidence occurring within each subject's healthcare facility and country. A list of additional covariates to be considered can be found in Table 5.4.1. For each subject in the control group, the index date (ie. time of first known exposure to COVID-19 patients) will be used as time zero. For HCWs that are treated with prophylaxis at any time their index date will be 7 days after initiation of treatment. Having an index date near treatment initiation will prevent the introduction of survivorship bias into the analysis.

Table 5.4.1 Model Covariates

Time-fixed/Time-varying Covariate	Covariate Name
Time-fixed Covariates	Healthcare facility, Country, Age, Biological Gender, BMI, Smoking status, Ethnicity, Blood type, Primary work location, Type of healthcare worker, Medical history

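### Dropping all but one of any highly correlated covariates gains the prophylaxis hazard ratio almost nothing, can leave residual confounding, and turns a kept risk factor's hazard ratio into a joint effect

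*SAP*

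**What the plan says.** SAP 6.4.1 fits a Cox model with a subject-level random effect. Facility and country are forced in. Other covariates pass a univariate screen ("any covariates with a p-value less than 0.20 will be included in a multivariate model") and then backward removal until all that remain are significant at the 0.10 level.

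The note under Table 5.4.1 adds a second, independent filter. First, "A correlation analysis will be completed to assess the level of correlation between variables"; then, "if a high level of correlation is found only one of the variables will be included as a covariate in the models". The note names no correlation measure, no threshold and no rule for choosing the survivor, and it does not exempt confounders.

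The time-varying rows of the table hold several groups of items that are likely to move together. They include "Mask usage, Gown usage, Eye protection usage, Glove usage", three patient-contact items (direct care, face-to-face contact, aerosol-generating procedures) and three household items.

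The sentence before the rule leaves another route open: "The necessity to create composite variables or collapse categories within variables will be determined upon the completion of the descriptive analyses".

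SAP 6.5 serves the risk-factor objective by taking the covariates left in the final primary model and testing each in turn with a likelihood ratio test. SAP 2.2 names PPE use and COVID-19 exposure among the factors to explore.

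**The concern.** The rule treats correlation among adjustment covariates as a fault in the model. For the prophylaxis HR it is not one. Collinearity between mask and gown inflates the variances of the mask and gown coefficients. The variance of the prophylaxis coefficient depends on how well all the covariates together predict prophylaxis, and a second, correlated item hardly changes that.

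Two things are at stake. The primary adjusted HR can keep confounding that the measured data could have removed. And the risk-factor analysis can credit one PPE or contact item with the effect of another, while the item that was removed never reaches the test in SAP 6.5. The registry aims to inform policy on prevention measures, so which item appears protective matters.

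The rule is also separate from the p-value selection. Repairing that selection would leave this filter in place.

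**Working it through.** **The plan's own figure.** The documents give no number for this rule. The nearest stated figure is the sample size in SAP section 5: 10,000 workers, 20% unexposed, 10% risk in the unexposed, 80% power for relative risk 0.78. Expected events are 2,000 × 0.10 + 8,000 × 0.078 = 824. Schoenfeld's formula gives |ln 0.78| × √(824 × 0.2 × 0.8) − 1.96 = 2.85 − 1.96 = 0.89, so power is 81.4%, close to the stated 80%. This figure does not depend on the rule; it only anchors the inputs.

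**Inputs.** From the SAP: N = 10,000, 80% treated, 10% risk in the untreated, two-sided 5%. Assumed: 70% always wear a mask and 70% always wear a gown, with correlation φ; mask HR 0.50, gown HR 1.00, drug HR 1.00; mask wearers have twice the odds of prophylaxis. The last assumption with 80% treated gives P(treated) = 0.835 with a mask and 0.717 without.

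**Kept item, by hand.** P(mask | gown) = 0.7 + 0.3φ and P(mask | no gown) = 0.7(1 − φ). A worker's mean relative rate is 1 − 0.5 × P(mask). With mask dropped, the gown rate ratio is therefore about (0.65 − 0.15φ)/(0.65 + 0.35φ). At φ = 0.70 this is 0.545/0.895 = 0.61. At φ = 0.90 it is 0.515/0.965 = 0.53.

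**Prophylaxis, by hand at φ = 0.70.**
- Gown wearers: P(mask) is 0.91 overall, 0.922 in the treated and 0.855 in the untreated. The rate ratio is (1 − 0.461)/(1 − 0.4275) = 0.94.
- Workers without a gown: P(mask) is 0.21 overall, 0.236 in the treated and 0.134 in the untreated. The rate ratio is (1 − 0.118)/(1 − 0.067) = 0.945.
- Adjusting for gown alone, an inert drug therefore shows HR about 0.94.

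**Model.** An expected-value Poisson rate model with exponential event times, under the same inputs, gives:

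| φ | Prophylaxis HR, both kept | Prophylaxis HR, mask dropped | Prophylaxis HR, gown dropped | Gown HR, mask dropped |
|---|---|---|---|---|
| 0.70 | 1.00 | 0.943 | 1.00 | 0.612 |
| 0.80 | 1.00 | 0.960 | 1.00 | 0.572 |
| 0.90 | 1.00 | 0.979 | 1.00 | 0.535 |
| 0.95 | 1.00 | 0.989 | 1.00 | 0.517 |

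The true gown HR is 1.00 in every row.

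**Precision at φ = 0.70.** The SE of the prophylaxis log HR is 0.081 with both items and 0.080 with mask dropped. The SE of each PPE item is 0.095 with both kept and about 0.067 with one.

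**Consequence for the test at φ = 0.70.** The shift is ln 0.943 = −0.059, and 0.059/0.080 = 0.73 SE. The chance of a nominally significant result for an inert drug is Φ(−1.96 + 0.73) + Φ(−1.96 − 0.73), about 11% instead of 5%. At φ = 0.90 it is about 6%.

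**Other assumptions.** Take two items with prevalence 0.5, each with infection HR 1.5 and treatment odds ratio 2, and a true prophylaxis HR of 0.78. Dropping one item gives 0.810 at φ = 0.70 and 0.786 at φ = 0.95, and the kept item's HR moves from 1.50 to 1.98 and 2.20. If the dropped item has HR 2 and odds ratio 3, the prophylaxis HR becomes 0.865 and 0.797. If it has HR 2 and odds ratio 0.5, the HR moves the other way, to 0.739 at φ = 0.70. If the dropped item lacks either link, the bias is zero.

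**The case against.** The best defence is that the rule applies only to high correlation, where it does least damage to the primary estimate. With neither PPE item in the model the inert drug shows HR 0.892. Keeping the gown as a proxy removes 1 − ln 0.943/ln 0.892 = 49% of that log-scale bias at correlation 0.70, and 1 − ln 0.979/ln 0.892 = 81% at 0.90. If the non-causal item is the one removed, nothing is lost. All of this stands. A reader might infer that the rule always leaves confounding; the documents do not support that. They give no correlations or effects, and they do not say which item stays. Equally, with no cut-off stated, correlations near 0.70 are not excluded.

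A reader might also infer that pruning brings no precision at all. That holds for the prophylaxis HR only. The kept item's own SE falls by 1 − 0.067/0.095 = 29% at correlation 0.70. But the narrower interval then describes the combined effect of both items.

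The same note allows composites, and SAP 6.3.8 already plans a count of items always used ("among mask, eye protection, gown, gloves will also be summarized: none, one, two, three, all four"). That is a fair point about the remedy. As written, though, composites are only a possibility to be decided after the descriptive analyses, while single-variable retention is the stated commitment.

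SAP 7.1 and 7.5 point to inverse probability weighting in a section 5.4.2. The SAP's contents list and text show only 6.4.1 under the primary analysis, so that cannot be relied on.

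Finally, the protocol (8.7.4 and 8.7.6) foresees that infections may be few, which argues for fewer terms. A pre-specified composite also saves terms, without an undefined choice of survivor.

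**Conclusion.** The concern holds in a limited form. For the primary analysis the rule buys almost nothing (SE 0.080 against 0.081) and can bias the prophylaxis HR, provided that the dropped item is related to both prophylaxis and infection given the kept one. In the base scenario the inert-drug HR is about 0.94 at correlation 0.70 and 0.98 at 0.90. Across the other scenarios the shift ranges from zero to about 11% (0.865/0.78 = 1.109), in either direction.

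The risk-factor objective suffers more, because there the distortion grows with correlation: the inert gown's HR goes from about 0.61 at 0.70 to about 0.54 at 0.90. The dropped item is never tested.

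The size rests on assumed correlations, prevalences and effects, and the calculation omits the subject frailty and time-varying values. A reader might conclude that every covariate in Table 5.4.1 must be kept. This point does not show that: the table lists candidate covariates without establishing each as a confounder, and the p-value selection is a separate matter.

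**What to change.** Change the note under Table 5.4.1 so that, in the prophylaxis model, no covariate is removed because it correlates with another, except where one is an exact alias of the other.

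For the risk-factor objective in SAP 6.5, test the correlated PPE items as one block and the patient-contact items as another, each with a joint likelihood ratio test. Alternatively, commit before the analysis to a composite, such as the 0–4 count of PPE items always used from SAP 6.3.8. State that the HR of a single item standing in for a correlated group is not to be read as that item's own effect.

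This is a change of SAP wording and needs no new data. The price is wider intervals for individual PPE and contact items: in the scenario above, the SE of the mask log HR rises from about 0.067 alone to about 0.095 with the gown also in the model.
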